receiving the 12 mg BID) or placebo. Patients in Part A, Period 2 will stay on their assigned dose for a maximum of 24 weeks or until they meet the criteria for loss of regrowth maintenance (LOM), defined as an absolute SALT score  $>20$ . Any patient meeting the LOM criteria at any assessment timepoint during Part A, Period 2 will enter Part B of the study and return to their original CTP-543 treatment from Part A, Period 1 (8 mg BID or 12 mg BID). Patients not meeting the LOM criteria (e.g., their absolute SALT score  $\leq 20$ ) at the end of 24 weeks will have the opportunity to continue receiving treatment in the Open-Label Extension study (CP543.5001) or they will complete treatment at Week 24 and return in 4 weeks for the Post-Treatment Safety Follow-up. The study design is depicted in the Study Flow Chart of the Appendix (Section 15.1).

An interim analysis to support regulatory activities related to an upcoming CTP-543 New Drug Application (NDA) submission will be conducted. The focus of the interim analyses will be on safety data and will occur following completion of Part A, Period 1. Additionally, after Part A, Period 1 completion, a PK population analysis will be completed. The PK analysis will be conducted by an outside vendor. This analysis will be described in a separate analysis plan and a separate report will be generated.

The primary efficacy assessment will be conducted when all patients have completed Part A, Period 2. An analysis of safety data will also be conducted. This analysis will be included in the NDA submission as an abbreviated report. Site personnel and patients will remain blinded to individual patient study treatments.

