#### 4. GENERAL ANALYSIS AND REPORTING CONVENTIONS

The following is a list of general analysis and reporting conventions to be applied to this study, unless otherwise specified. Departures from these general policies will be described, if applicable, in the appropriate sections of this SAP. When this situation occurs, the rules set forth in the specific section take precedence over the general policies.

All data displays (tables, listings, and figures) will have a header showing the sponsor company name, protocol number, page number, and display status (i.e. “DRAFT” or “FINAL”), as well as a footer indicating file name and run date/time. Summary tables and data listings will be summarized by treatment group for efficacy and exposure, and by treatment group and overall otherwise. All data for analysis may be listed by-patient.

Specifically, for each Part and Period of the study, the summary table layout will be as follows:

For Part A, Period 1 tables:

Treatment Phase		
CTP-543 8 mg BID	CTP-543 12 mg BID	Total

For Part A, Period 2 tables:

Dose Reduction		Drug Discontinuation		Total
CTP-543 8 mg BID to 4 mg BID	CTP-543 12 mg BID to 8 mg BID	CTP-543 8 mg BID to Placebo	CTP-543 12 mg BID to Placebo	

For Part B tables:

Dose Reduction		Drug Discontinuation		Total
CTP-543 8 mg BID to 4mg BID to 8 mg BID	CTP-543 12 mg BID to 8 mg BID to 12 mg BID	CTP-543 8mg BID to Placebo to 8 mg BID	CTP-543 12 mg BID to Placebo to 12 mg BID	

Note that for all efficacy and exposure tables, the total column will not be displayed.

Categorical variables will be summarized using counts (n) and percentages (%) and will be presented in the form “n (xx.x).” If a count is 0, no percentage will be shown. If a percentage is 100%, 100 will be shown. To ensure completeness, summaries for categorical variables will include all categories, even if no patients had a response in a particular category. Unless otherwise specified, the denominator for each percentage will be based on the number of patients in the population being summarized (header n). Percentages will be rounded to one decimal place.

Continuous variables will be summarized using mean, standard deviation, minimum, maximum, median, and number of patients. The minimum and maximum will be the same precision as the

Concert Pharmaceuticals, Inc.  
Statistical Analysis Plan – CP543.2004

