## **5. ANALYSIS SAMPLES**

The Efficacy Population will include all patients who are randomized in the study, dispensed study drug, and have at least 1 post-treatment SALT assessment.

The Safety Population will include all patients who receive study drug during the Treatment Period.

The Pharmacokinetic (PK) population will include all patients who received study drug in Part A, Period 1 and had at least 1 post-treatment blood draw.

All populations will be analyzed by the treatment received. In the event patients incorrectly receive treatment associated with a different treatment group per Part and/or Period of the study, they will be analyzed “as treated” if the patient received that treatment for more than 50% of doses for that Period/Part.

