Finally, the count and percentage of abnormal laboratory values per parameter, where applicable, will be provided. Additionally, a listing of patients with Abnormal laboratory values will be provided.

These analyses will be repeated for serum chemistry results, hematology results, and lipid results (where lipid tests include total cholesterol, low-density lipoprotein, high-density lipoprotein, and triglycerides). Laboratory results will also be listed. Reference ranges for each clinical laboratory parameter will also be summarized in a data listing.

Pregnancy test results will be listed only.

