### **9.6.2. Physical Examinations**

A complete physical examination will consist of an examination of all major organ systems to include, but not be limited to, chest auscultation, abdominal auscultation and palpation, head, eyes, ears, nose and throat. An assessment for active signs and symptoms of infection including tuberculosis and skin examinations for non-melanoma skin cancers will be performed.

Evaluation for progressive multifocal leukoencephalopathy symptoms such as facial droop, general weakness, clumsiness, trouble speaking, personality changes, memory problems, and vision changes will be assessed.

Additionally, an assessment for the presence or absence of nasal hair will be performed during complete physical exams. Presence or absence of nasal hair will be summarized at baseline, Week 24 (Part A Period 1), Week 48 (Part A Period 2), and Week 24 (Part B). The presence or absence of nasal hair will be summarized as counts and percentages by treatment group and visit for the Safety Population, for each Part/Period of the study.

Brief physical examinations will include assessment for active signs and symptoms of infection, including tuberculosis, skin examinations for non-melanoma skin, and an evaluation for PML symptoms such as facial droop, general weakness, clumsiness, trouble speaking, personality changes, memory problems, and vision changes. Brief physical examinations will be performed according the Schedule of Events (Appendix 15.2).

A listing of the date and type of physical examinations performed will be provided. The listing will include presence or absence of nasal hair. Deteriorations from baseline on physical examination will be coded as adverse events and summarized as such.

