Table	14.3.4.4.3	Summary of Treatment-Emergent Potentially Clinically Significant Clinical Laboratory Values: Hematology — Part B	Safety Population	
Table	14.3.4.5.1	Summary of Treatment-Emergent Potentially Clinically Significant Clinical Laboratory Values: Serum Chemistry — Part A Period 1	Safety Population	Y
Table	14.3.4.5.2	Summary of Treatment-Emergent Potentially Clinically Significant Clinical Laboratory Values: Serum Chemistry — Part A Period 2	Safety Population	Y
Table	14.3.4.5.3	Summary of Treatment-Emergent Potentially Clinically Significant Clinical Laboratory Values: Serum Chemistry — Part B	Safety Population	
Table	14.3.4.6.1	Summary of Treatment-Emergent Potentially Clinically Significant Clinical Laboratory Values: Lipids — Part A Period 1	Safety Population	Y
Table	14.3.4.6.2	Summary of Treatment-Emergent Potentially Clinically Significant Clinical Laboratory Values: Lipids — Part A Period 2	Safety Population	Y
Table	14.3.4.6.3	Summary of Treatment-Emergent Potentially Clinically Significant Clinical Laboratory Values: Lipids — Part B	Safety Population	
Table	14.3.4.7.1	Summary of Abnormal Clinical Laboratory Values by Treatment Group and Visit: Hematology — Part A Period 1	Safety Population	Y
Table	14.3.4.7.2	Summary of Abnormal Clinical Laboratory Values by Treatment Group and Visit: Hematology — Part A Period 2	Safety Population	Y
Table	14.3.4.7.3	Summary of Abnormal Clinical Laboratory Values by Treatment Group and Visit: Hematology — Part B	Safety Population	
Table	14.3.4.8.1	Summary of Abnormal Clinical Laboratory Values by Treatment Group and Visit: Serum Chemistry — Part A Period 1	Safety Population	Y

Concert Pharmaceuticals, Inc.  
Statistical Analysis Plan – CP543.2004

Type	Number	Title	Population	For abbreviated report?
Table	14.3.4.8.2	Summary of Abnormal Clinical Laboratory Values by Treatment Group and Visit: Serum Chemistry — Part A Period 2	Safety Population	Y
Table	14.3.4.8.3	Summary of Abnormal Clinical Laboratory Values by Treatment Group and Visit: Serum Chemistry — Part B	Safety Population	
Table	14.3.4.9.1	Summary of Abnormal Clinical Laboratory Values by Treatment Group and Visit: Lipids — Part A Period 1	Safety Population	Y
Table	14.3.4.9.2	Summary of Abnormal Clinical Laboratory Values by Treatment Group and Visit: Lipids — Part A Period 2	Safety Population	Y
Table	14.3.4.9.3	Summary of Abnormal Clinical Laboratory Values by Treatment Group and Visit: Lipids — Part B	Safety Population	

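### Under the SAP's default denominator, Week 48 nasal-hair percentages in Period 2, and by-visit laboratory-abnormality percentages if counted per patient, shrink as patients leave for loss of maintenance

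*SAP*

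**What the plan says.** SAP Section 4 fixes the denominator for all percentages: "Unless otherwise specified, the denominator for each percentage will be based on the number of patients in the population being summarized (header n"). It allows exceptions: where a section departs from the general conventions, "the rules set forth in the specific section take precedence over the general policies".

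Neither relevant section states an exception. On laboratory abnormalities, Section 9.5 says that "the count and percentage of abnormal laboratory values per parameter, where applicable, will be provided". On nasal hair, Section 9.6.2 says: "The presence or absence of nasal hair will be summarized as counts and percentages by treatment group and visit for the Safety Population". The only Period 2 time point it names for nasal hair is Week 48.

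The list of outputs in Section 15.4 has separate Period 2 tables for these summaries, laid out by visit. One example is "Summary of Abnormal Clinical Laboratory Values by Treatment Group and Visit: Hematology — Part A Period 2" (Table 14.3.4.7.2). Tables 14.3.4.8.2 (chemistry), 14.3.4.9.2 (lipids) and 14.3.5.2.2 (nasal hair) follow the same pattern. All four use the Safety Population, and all four are marked for the abbreviated report that supports the NDA.

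Membership of that population does not depend on having data at a visit: "The Safety Population will include all patients who receive study drug during the Treatment Period". Period 2 follow-up, however, ends at LOM: "Any patient meeting the LOM criteria at any assessment timepoint during Part A, Period 2 will enter Part B of the study". SAP Section 8.1.2 then counts Part B assessments from the Part B start date, so they do not return to Period 2 visits.

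**The concern.** A patient who reaches LOM at Period 2 Week 4 cannot contribute an abnormal laboratory result at Period 2 Weeks 8 to 24, or a nasal-hair finding at Week 48. The same patient remains in the header n. The numerator then comes from those still in Period 2 and the denominator from everyone who entered the arm.

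This is not sporadic missingness. The exit is part of the design and is triggered by the primary outcome. The amount of exit may well differ by arm: Protocol Section 5.2.1 refers to evidence that stopping a JAK inhibitor after regrowth leads to loss of the regrown hair. If so, the arm losing more hair would show fewer laboratory abnormalities at late visits even with identical rates among those assessed. A reader of the abbreviated report could take that for a safety difference.

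**Working it through.** **Header n.** Protocol Section 13.1 aims for about 50 Responders per dose group, and Section 8.3 randomizes them 1:1. That gives 50 × 1/2 = 25 per arm, which agrees with the stated figure of about 25. This is the number the default would put under each Period 2 percentage.

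**When observation stops.** Footnote 14 of Protocol Table 1 requires the Period 2 safety assessments before Part B drug is dispensed, so a patient is still assessed at the LOM visit. The loss starts at the next visit. The affected visits are:

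- hematology and chemistry: any scheduled Period 2 visit after a LOM exit;
- lipids: Weeks 36 and 48, the only Period 2 lipid visits in Protocol Table 1;
- nasal hair: Week 48 only.

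**Formula.** Let N be the header n, L the share of the arm with LOM before the visit, and p the proportion with the finding among those assessed. Ignoring other dropout, N(1 − L) patients are assessed and pN(1 − L) have the finding.

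- Header-n percentage = pN(1 − L)/N = p(1 − L)
- Assessed-n percentage = pN(1 − L)/[N(1 − L)] = p

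**One arm, N = 25.** The documents give neither L nor p. I assume p = 20% for a laboratory abnormality and p = 80% for nasal hair present.

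| LOM before the visit | Laboratory abnormality, header n | Nasal hair present, header n |
|---|---|---|
| 0% | 20.0% | 80.0% |
| 10% | 18.0% | 72.0% |
| 20% | 16.0% | 64.0% |
| 40% | 12.0% | 48.0% |
| 60% | 8.0% | 32.0% |
| 80% | 4.0% | 16.0% |

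With assessed n, every row would read 20.0% and 80.0%.

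**Two arms at Week 48.** Assume LOM before Week 48 in 5/25 on dose reduction and 15/25 on discontinuation, with the same p in both arms.

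| | Dose reduction (20 assessed) | Discontinuation (10 assessed) |
|---|---|---|
| Laboratory abnormality, header n | 4/25 = 16.0% | 2/25 = 8.0% |
| Laboratory abnormality, assessed n | 4/20 = 20.0% | 2/10 = 20.0% |
| Nasal hair present, header n | 16/25 = 64.0% | 8/25 = 32.0% |
| Nasal hair present, assessed n | 16/20 = 80.0% | 8/10 = 80.0% |

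The header-n rows show gaps of 8 and 32 points where the rates among those assessed are equal. Nasal hair present and absent together add to 64.0 + 16.0 = 80% in one arm and 32.0 + 8.0 = 40% in the other, which is 1 − L in each.

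**Unit of the laboratory count.** Section 9.5 speaks of abnormal values, while header n counts patients. If the tables count values over values obtained, the shrinkage does not occur. If they count patients, the default applies and it does. The SAP does not say which. For nasal hair, present or absent is a patient-level finding, so the default applies without this doubt.

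**The case against.** The strongest reply is that the default is only a default. By-visit denominators are often settled in table shells, and SAP Section 4 promises mock tables. A percentage of values also suggests values obtained as the denominator. This stands as a limit on certainty for the three laboratory tables: the documents do not establish that they will be divided by the whole arm. It does not settle the matter, because Section 16 lists no attachments and the text gives no other denominator. Section 6.1 shows that special denominators are written out where they are wanted.

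Second, the reader is not blind. Counts print beside percentages, the Period 2 mean-change tables report the number of patients, laboratory data are listed, and nasal-hair categories that fail to reach 100% reveal the shortfall. All of this is true, but it leaves the reader to rebuild the percentage by hand.

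Third, these are secondary descriptive outputs. No hypothesis is tested, no between-arm comparison of these percentages is planned, and nasal hair was added in the SAP. The treatment-emergent PCS and adverse-event tables count patients over the whole Part or Period, and the mean changes and hematology box plots use observed values. None of these is distorted in this way. This limits the importance of the point.

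Fourth, a corrected denominator does not make late visits comparable. Those still assessed are selected by not having had LOM. With 80% LOM in an arm of 25, 5 remain, and 1/5 = 20% has an exact 95% interval of about 0.5% to 72%. This is right, and the fix should say so.

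**Conclusion.** The point holds as a denominator problem of limited reach. Under the stated default, nasal-hair percentages at Week 48 are multiplied by 1 − L. So are the by-visit laboratory-abnormality percentages in Period 2 if they are counted per patient. The proportional shrinkage is greater in the arm with more LOM. That direction is algebra. The size is not known: 16% versus 8% rests on assumed LOM of 20% and 60%, an assumed 20% rate among those assessed in both arms, and no other dropout.

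A reader might infer more, and the documents do not support it:

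- That all the laboratory percentages certainly use the whole arm. The unit is ambiguous.
- That equal rates will appear as a four-fold difference. That needs assumed LOM of 20% and 80%, since (1 − 0.2)/(1 − 0.8) = 4, and the documents give no LOM rates.
- That the Period 2 safety assessment as a whole is compromised. The per-patient PCS, adverse-event and mean-change summaries are outside this problem.
- That changing the denominator restores a randomized comparison at late visits. It removes the arithmetic artefact and leaves the selection.

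**What to change.** Add to SAP Sections 9.5 and 9.6.2 that the by-visit percentages are counted per patient, and that the denominator is the number of patients with a non-missing assessment of that parameter at that visit in that Part/Period. Print that n at each visit in Tables 14.3.4.7.2, 14.3.4.8.2, 14.3.4.9.2 and 14.3.5.2.2.

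Add a footnote to the same tables: later Period 2 visits include only patients who have not left for LOM, so differences between arms at those visits are not randomized comparisons.

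The cost is a short SAP addition, a denominator change in the table programs and a footnote. Data collection and conduct do not change. The downside is that late-visit percentages will rest on visibly small numbers.

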- For patients who are ongoing, date of last dose will be imputed as the data cut date.

Summary tables and data listings:

- No preliminary rounding will be performed; rounding will only occur after analysis. Note that for the clinical purposes of moving patients through parts and periods, SALT scores were rounded to the nearest integer prior to determining the SALT  $\leq 20$  criterion.
- Data from patients excluded from an analysis population will be presented in the data listings but will not be included in the calculation of summary statistics, where applicable.

Concert Pharmaceuticals, Inc.  
Statistical Analysis Plan – CP543.2004

- Data from each patient will be separated by a blank line. Within a data listing, if a descriptive item appears line after line (e.g., repetition of a patient number, date, visit, etc.), only the first occurrence will be displayed (e.g., in Listing of Vital Signs, patient number, date and visit will only be displayed on first row when presenting all parameters collected at same visit). Repetition of actual results or outcomes (e.g., adverse events, lab results, vital sign values, etc.) will not be collapsed.
- Data listings will be sorted by treatment, patient, and date and/or time of assessment, as applicable. Data listings may be separated by study part.
- There will be 3 baselines in this study, defined as follows:
  - Part A Period 1 baseline is the last observation obtained on or before the day of dosing of study drug in Part A Period 1.
  - Part A Period 2 baseline is the last observation obtained on or before the day of dosing of study drug in Part A Period 2.
  - Part B baseline is the last observation obtained on or before the day of dosing of study drug in Part B.
- Unless otherwise noted, values reported as greater than or less than some quantifiable limit (e.g., “< 2.0”) will be summarized as using the numeric equivalent in summary tables and figures (e.g. “<2.0” will be analyzed as 2.0). The reported value will be used in listings.

Mock tables and data listings will be provided as attachments to this analysis plan. Minor changes to the mocks after formal SAP approval will not necessitate re-approval unless changes to the text of the SAP are required.

All statistical deliverables will be produced, validated, and reviewed for accuracy/consistency in accordance with [REDACTED] standard operating procedures and the processes described in the statistical validation plan.

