## 6.2. Demographic and Other Baseline Characteristics

Demographic characteristics (i.e., sex, ethnic origin, race, age, and calculated body mass index) will be collected at the Screening Visit, between Day -28 and -1, and detailed on the eCRF.

Demographic characteristics will be summarized using descriptive statistics for all randomized patients by treatment group and overall, for each of Part A Period 1, Part A Period 2, and Part B.

Concert Pharmaceuticals, Inc.  
Statistical Analysis Plan – CP543.2004

Baseline characteristics will be summarized using descriptive statistics for all randomized patients by treatment group and overall, for each study part, and will include the following:

- Baseline total SALT score
  - Note: Baseline total SALT score for Part A Period 2 will be the last SALT score obtained prior to dosing in Part A, Period 2 (ie, Week 24 SALT assessment from Part A, Period 1). Part B baseline total SALT score will be the last SALT score obtained in Part A, Period 2 prior to re-randomization into Part B.
- Alopecia areata classification (randomization strata): partial scalp hair loss (SALT  $\geq$  50 and < 95); complete or near-complete scalp hair loss (SALT  $\geq$  95)
- duration of current episode in years (calculated as: [date of randomization – date of current episode onset + 1] / 365.25)
- nasal hair involvement

For Part A Period 1, whether the patient has experienced any past and/or concomitant diseases, conditions, or exposures to serious infections (such as HIV), or past surgeries will also be summarized with baseline characteristics.

Other co-morbidities may be identified and included as baseline characteristics.

All demographics and baseline characteristics will also be listed within a by-patient data listing for all randomized patients.

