## **8.2. Primary Endpoints**

### Part A:

This study is designed to be exploratory and descriptive in nature and no formal hypothesis testing is planned. Therefore, descriptive statistics will be used to summarize the results regarding dose modification following successful hair regrowth for each dose group. In Part A, Period 1, a Responder is defined as having an absolute SALT score  $\leq 20$  at Week 24 of the Treatment Period. Only Responders will enter into Part A, Period 2 (Dose Modification) for the primary efficacy analysis. For Part A of the study, there are two co-primary efficacy endpoints. The first co-primary efficacy endpoint is the percentage of patients achieving LOM criteria (SALT  $> 20$ ) compared to the percentage of patients maintaining treatment success (SALT  $\leq 20$ ) for each of the following dose reduction conditions (Period 2 ONLY):

- 12 mg BID reduced to 8 mg BID
- 8 mg BID reduced to 4 mg BID

The second co-primary efficacy analysis is the percentage of patients achieving LOM criteria compared to the percentage of patients maintaining treatment success for each of the following drug discontinuation conditions (Period 2 ONLY):

- 12 mg BID to Placebo
- 8 mg BID to Placebo

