### **8.2.1. Computation of the Primary Endpoints**

The SALT is a measure of hair loss that quantifies the amount of scalp surface without hair in a pre-specified quadrant of the scalp (right side, top, left side, back), that is further summed after applying a quadrant-specific multiplier indicative of scalp surface area contribution, to provide an overall score of total hair loss. An example of the SALT assessment can be found in Appendix 18.2 of protocol.

The primary endpoints for each Part of the study consist of deriving and categorizing the individual overall SALT scores ( $\leq 20$  versus  $> 20$ ).

Due to the variable time on study for each patient within Part A Period 2, the primary analysis visit will be the End of Part A Period 2, where the last observed non-missing SALT value is selected for each patient. Otherwise, missing data will not be imputed for this descriptive, exploratory study.

Patterns of missing values across visits will be listed and summarized with numbers and percentages by treatment and visit.

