### **8.2.3. Sensitivity Analyses of the Primary Analysis**

No sensitivity analyses specified.

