#### 8.4.1. Secondary SALT Endpoints

The following secondary SALT responder endpoints will be assessed:

Part A

- Percentage of patients achieving LOM criteria (SALT > 20) for each *dose reduction* condition at Weeks 4, 8, 12, 16, 20, and 24 (Period 2 ONLY). Note that these timepoints in Period 2 are equivalent to Weeks 28, 32, 36, 40, 44, and 48, respectively.
- Percentage of patients achieving LOM criteria (SALT > 20) for each *drug discontinuation* condition at Weeks 4, 8, 12, 16, 20, and 24 (Period 2 ONLY). Note that these timepoints in Period 2 are equivalent to Weeks 28, 32, 36, 40, 44, and 48, respectively.
- Percentage of patients achieving an absolute SALT score  $\leq 20$  at Weeks 4, 8, 12, 16, 20, and 24 (Period 1 ONLY)
- Relative change in SALT scores from Baseline at Weeks 4, 8, 12, 16, 20, and 24 (Period 1 ONLY)

Part B:

- Percentage of patients achieving the ROR criteria (SALT  $\leq 20$ ) at Weeks 4, 8, 12, 16, and 20
- Relative change in SALT scores from Part B Baseline at Weeks 4, 8, 12, 16, 20, and 24

Concert Pharmaceuticals, Inc.  
Statistical Analysis Plan – CP543.2004

Secondary endpoints on percentage of patients achieving an absolute SALT score of  $\leq 20$  or SALT  $> 20$ , will be assessed according to Section 8.4.

The continuous secondary SALT endpoint of relative change in SALT score from baseline at Weeks 4, 8, 12, 16, 20, and 24 in Part A Period 1 will be assessed with an MMRM, according to Section 8.4. The baseline SALT score will be as follows for each endpoint per Part:

Relative reduction is based on relative change from baseline.

Relative change in SALT score is derived as percent change of the follow-up SALT score, where baseline SALT score is the denominator (i.e. absolute change divided by the baseline score, multiplied by 100).

In addition, summary statistics for the mean, mean change, and mean relative change in total SALT score from Part A Period 1 baseline will be reported for Part A Period 1, Part A Period 2, and Part B. The mean and mean change in total SALT score from Part A Period 2 baseline will be reported for Part A Period 2 and Part B. Mean relative change from Part A Period 2 baseline will not be calculated as baseline values may be zero by design and would result in undefined relative changes. The mean, mean change, and mean relative change in total SALT score from Part B baseline will be reported for Part B.

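### Patients were moved on integer-rounded SALT but are analysed on unrounded SALT, so a score above 20 and below 20.5 can be a loss of maintenance on paper only; no planned output gives the exact number

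*SAP*

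**What the plan says.** SAP section 4 puts two rules in one bullet. For analysis: "No preliminary rounding will be performed; rounding will only occur after analysis". For moving patients through parts and periods: "SALT scores were rounded to the nearest integer prior to determining the SALT" criterion of 20 or less was applied. The same section lets later sections depart from its conventions: "When this situation occurs, the rules set forth in the specific section take precedence over the general policies".

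The sections that could depart from it do not:

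- SAP 8.2, Part A, defines a Responder as SALT of 20 or less at Week 24 and states: "Only Responders will enter into Part A, Period 2 (Dose Modification) for the primary efficacy analysis".
- SAP 8.2.1 splits SALT at 20 and, for Period 2, says that "the last observed non-missing SALT value is selected for each patient".
- SAP 8.4.1 lists, by visit, "Percentage of patients achieving LOM criteria (SALT > 20) for each" dose-reduction and discontinuation condition.
- SAP 8.5.1 dates first LOM at the first Period 2 score above 20.
- SAP 8.2.3 reads: "No sensitivity analyses specified".

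Protocol 8.1 and footnotes 14 and 15 of protocol Table 1 give the movement rule as above 20 versus 20 or less, with no mention of rounding. SAP section 13 does not list rounding among the changes from the protocol. Protocol 11.2 refers SALT scoring details to a Site Operations Manual, which is not among the documents.

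**The concern.** Rounding to the nearest integer turns any score above 20 and below 20.5 into 20, which meets the movement criterion. Unrounded, the same score is above 20 and counts as LOM. Three consequences follow from the stated rules alone:

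1. **Entry.** A patient at 20.2 at Week 24 passes the movement check and enters Period 2, yet is a Non-Responder in the Period 1 tables. SAP 6.2 says "Baseline total SALT score for Part A Period 2 will be the last SALT score obtained prior to dosing", so the Period 2 baseline is 20.2. If the score is still 20.2 at Week 4, the patient is a first-LOM event with no change from that baseline.
2. **During Period 2.** A mid-period score in the band is LOM at that visit and an event in the Kaplan-Meier analysis, while the patient stays in Period 2.
3. **Co-primary.** If the last score is in the band, the patient is LOM without having met the movement criterion for Part B. If a later last score is 20 or less, the patient counts as maintained in Table 14.2.1.1 and as an event in Table 14.2.4.1.

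In a descriptive study the LOM percentages and curves are the result, and they go into the abbreviated report for the NDA. A reader should be able to see how many LOM events exist only because of the rounding difference.

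**Working it through.** **Plan's own figure.** Protocol 13.1 expects about 50 Responders per dose group, randomized 1:1: 50 × 1/2 = 25 per arm. This reproduces. There is no power calculation to check.

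**Is the band attainable?** Protocol 18.2 gives SALT = 0.18 × left + 0.18 × right + 0.40 × top + 0.24 × back. I enumerated all combinations.

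- Quadrants scored in 1% steps: 24 totals lie strictly between 20 and 20.5 (20.02 to 20.48).
- 5% steps: 4 totals (20.1, 20.2, 20.3, 20.4).
- Example: 15/15/25/20 gives 2.70 + 2.70 + 10.00 + 4.80 = 20.20.
- Exactly 20.5 is also attainable: 5/0/10/65 gives 0.90 + 0 + 4.00 + 15.60 = 20.50.

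**Timing of an event with no change.** SAP 8.5.1 uses (event date − randomization date + 1)/7. At the Week 4 visit this is (28 + 1)/7 = 4.1 weeks.

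**Weight of one patient.** 1/25 = 4.0 points. With the SAP 8.2.2 interval, p ± 1.96 × √(p(1 − p)/n) + 1/(2n) at n = 25:

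| LOM | % | 95% CI | Half-width |
|---|---|---|---|
| 10/25 | 40.0 | 18.8 to 61.2 | 21.2 points |
| 11/25 | 44.0 | 22.5 to 65.5 | 21.5 points |

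**Share entering above 20 (assumed start distributions on 0 to 20.5).**

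- Uniform: 0.5/20.5 = 2.4%.
- Weighted to low scores, 20.5 × Beta(1,2): (0.5/20.5)² = 0.06%.
- Weighted to high scores, 20.5 × Beta(2,1): 1 − (20/20.5)² = 4.8%.

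**Illustration over Period 2.** The documents give no distribution of SALT in Period 2, so every input here is an assumption. The model is a random walk over six visits, floored at 0, with the patient leaving at 20.5 or more. There are 45 scenarios: the three starts above, mean change per visit of 0, 0.5, 1, 2 or 5 points, and SD of 1.5, 3 or 4.

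| Quantity | Median | Range |
|---|---|---|
| Last value in the band (co-primary) | 0.75% | 0 to 2.7% |
| LOM event, but last value 20 or less | 0.8% | 0 to 2.4% |
| LOM status differs between rules (time to first LOM) | 1.9% | 0 to 3.6% |
| LOM date or status differs | 7.5% | 1.1 to 16% |
| Largest by-visit gap in cumulative LOM | 2.4 points | 0.6 to 4.0 points |

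Per arm of 25, the co-primary row is 25 × 0.0075 = 0.2 patient (0 to 25 × 0.027 = 0.7). The status row is 25 × 0.019 = 0.5 patient at the median. The rest of the 7.5% are patients who are LOM under both rules, at different visits.

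**The case against.** **The rules are disclosed and clear.** This stands. The SAP states both, and the unrounded analysis matches the protocol's literal threshold. A reader might infer that the analysis threshold is wrong or ambiguous; the documents do not support that. Disclosure does not, however, tell the reader how many patients are affected.

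**Cross-checks already exist.** This stands in part.

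- The Period 2 disposition table (14.1.1.2) counts patients who completed with LOM and entered Part B. It can be set against unrounded LOM in Table 14.2.1.1.
- Week 24 responders in Table 14.2.2.1 can be set against the number randomized into Period 2.
- Listing 16.2.6.1.3 shows individual scores.

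The table comparisons are net counts, blurred by discontinuation and non-entry, and they do not show shifted LOM dates. The listing requires counting by hand.

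**The effect is small.** This stands. The co-primary effect is under one patient per arm in every scenario, against a half-width of about 21 points. With a mean change of 5 points per visit, at most 0.43% of patients have a last value in the band.

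**The 7.5% overstates the issue.** This stands. A reader might take it as the share whose LOM status changes; it is mostly a change of date. The scenarios are a chosen grid, so their median is not an estimate for this trial.

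**Tables differ partly because endpoints differ.** This is true: by-visit status, first LOM and last value are separate, labelled definitions. A LOM event in a patient who never met the movement criterion still comes from the rounding difference.

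**The tie at 20.5 is peripheral.** This stands. A score of 20.5 is above 20 in every planned analysis, and the handling for movement may be in the Site Operations Manual.

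**Conclusion.** The mismatch is certain from the text; its size is not. The two rules permit LOM events that did not meet the movement criterion, including events with no hair loss since Period 2 entry, and no planned output gives their exact number. That some patient was in fact affected cannot be shown from the documents.

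Under the assumed scenarios, the co-primary effect is about 0 to 0.7 patient per arm of 25. For time to first LOM, status differs for a median of about 1.9% of patients, and the cumulative LOM percentage differs by 0.6 to 4.0 points at the worst visit.

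Two stronger readings are not supported. One is that the LOM results are unreliable: no test decision depends on them, and the expected shift lies well inside the interval width. The other is that patients were moved wrongly: the documents show only that the SAP's account of movement and the protocol's wording differ. The point is a cheap improvement to a descriptive analysis.

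**What to change.** Keep the unrounded analysis as primary, and add:

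- In SAP 8.2.3, one repeat of the co-primary LOM percentage using the rounded (movement) classification.
- In SAP 8.5.1, one repeat of time to first LOM using the same classification.
- A count by arm of patients whose rounded and unrounded classifications differ, with those entering Period 2 above 20 shown separately.
- For the rounded classification, a statement of how a score of exactly 20.5 was handled in practice.

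The account of movement in SAP section 4 and the wording in protocol 8.1 and the Table 1 footnotes must be reconciled. This review does not say which is right.

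The cost is one derived variable, a few rows in Tables 14.2.1.1 and 14.2.4.1, a second Kaplan-Meier run for four arms with its quantiles and median intervals, and a sentence in each of the two SAP sections. No new data are needed.
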